Sponsor	The sponsor is the party that commissions the organisation or performance of the research, for example a pharmaceutical company, academic hospital, scientific organisation or investigator. A party that provides funding for a study but does not commission it is not regarded as the sponsor, but referred to as a subsidising party.
SUSAR	Suspected Unexpected Serious Adverse Reaction
UAVG	Dutch Act on Implementation of the General Data Protection Regulation; in Dutch: Uitvoeringswet AVG
WMO	Medical Research Involving Human Subjects Act; in Dutch: Wet Medisch-wetenschappelijk Onderzoek met Mensen

SUMMARY

Rationale: To identify new, individualized, neuroprotective treatments for ischemic stroke, responses to ischemia of human neurons, including inter-individual variation, need clarification. By combining state of the art stem cell biology and organ-on-a-chip technology, we aim to derive neuronal networks of patients with brain infarcts and investigate the effects of simulated cerebral ischemia.

Objective: The primary objective is generation of functional neuronal networks from induced pluripotent stem cells (iPSCs) derived from patients with ischemic stroke. The secondary objectives are to measure neuronal network responses to simulated cerebral ischemia, estimate differences between patients and controls, and estimate variation amongst patients.

Study design: This will be a prospective, experimental, case-control study in human blood.

Study population: Ten adult patients with ischemic stroke will be included in this study. These patients have clearly documented cerebral infarcts. hiPSCs from five age-matched control subjects from our repository will be used as controls.

Study procedures: Collection of heparin diluted blood samples (30cc per subject). Blood samples will be used for derivation of neuronal networks in the laboratory. All subsequent experiments are with these neuronal networks in the lab. Patients will be treated according to local and national guideline for ischemic stroke. There will be no experimental / additional treatment for patients. Standard treatment or care will not be withheld.

Main study parameters/endpoints: Primary outcome measure is network functionality, where a network is considered functional when a minimum of 1/3 of the electrodes shows activity, with a minimum of 6 spikes per minute per active electrode, and a minimum of one synchronous event per minute at eight weeks after plating. Other study parameters include electrophysiological responses to simulated 'cerebral ischemia', and network and neuronal properties as studied by immunocytochemical analyses.

Nature and extent of the burden and risks associated with participation, benefit and group relatedness: Risks of blood sampling are considered negligible.

1. INTRODUCTION AND RATIONALE

Ischemic stroke: individualized treatable targets needed

Acute ischemic stroke is the leading cause of chronic adult disability and the third leading cause of death in the Western world.^{1,2} Epidemiological studies predict a rising incidence.¹ The only treatment of proven benefit to reduce neurological impairment is acute recanalization by intravenous thrombolysis (IVT) or intra-arterial thrombectomy (IAT).^{3,4} However, only ~30% of all patients are eligible for either IVT or IAT. Moreover, even with recanalization, recovery rates vary widely.⁴ New experimental stroke research on identification of new, individualized treatable targets is one of the three goals set by the European Stroke Organization for 2030.⁵

Patient variation incompletely understood

Even if complete revascularization is obtained, recovery of patients with acute ischemic stroke varies from complete recovery to persistent neurological deficit.⁶ Approximately one third recovers, whereas another third deteriorates with an increase of neurological deficit.⁷ In 2-10%, space-occupying edema formation causes severe deterioration or death.⁸ Variations in outcome cannot be fully explained by variations of (re)perfusion.⁹ Electrophysiological and biochemical mechanisms that may contribute to secondary damage or recovery include synaptic failure,¹⁰ cortical spreading depression,¹¹ excitotoxicity,¹² and formation of heat shock proteins.⁹ All these contributors vary substantially between brain areas within one patient and between patients.⁹⁻¹² This indicates possible differences between patients with regard to brain responses to ischemia.

Neuroprotection: poor extrapolation from animal studies to patients

Over the past two decades, >1200 experimental studies have been reported providing strong proof of principle that high grade protection of ischemic brain tissue is an attainable goal. Effective treatments included ion channel blockage, neurotransmitter antagonism, and suppression of inflammation.¹³ However, in >500 clinical trials, none of these therapies could be translated into clinical effectiveness in patients with ischemic stroke.¹³ One important, but underexposed, factor hampering demonstration of efficacy in patients with brain infarcts is the large heterogeneity of patient groups, where the pathophysiology of either recovery or deterioration often remains enigmatic.² To identify new, individualized, neuroprotective treatment, inter-individual differences of neuronal responses to ischemia, and causes hereto, need clarification.

Proposed solution: human in vitro model

By combining state of the art stem cell biology and organ-on-a-chip technology, we aim to investigate the effects of simulated cerebral ischemia on human neurons from patients with brain infarcts. We will collect blood from patients with ischemic stroke, derive stem cells, and differentiate into neuronal networks. Herewith, we obtain patient specific neuronal networks that will possibly reflect the inherent vulnerability to ischemia and to neuroprotective medication of a specific patient. Neuronal responses to ischemia and medication will be

related to clinical and neurophysiological properties. Herewith we will obtain insight into patient-specific vulnerability to ischemia and probably identify specific treatment targets.

2. OBJECTIVES

Primary Objective:

To generate functional neuronal networks from induced pluripotent stem cells (iPSCs) derived from patients with ischemic stroke

Secondary Objectives:

To measure neuronal network responses to simulated cerebral ischemia, estimate differences between patients and controls, and estimate variation amongst patients.

Tertiary Objectives

To relate ischemic responses to patient characteristics and to neuronal properties

3. STUDY DESIGN

This will be a prospective, experimental, case-control study in human blood.

4. STUDY POPULATION

4.1 Population (base)

Ten patients with ischemic stroke will be included in this study. These patients should have clearly documented cerebral infarcts, confirmed by MRI or CT imaging. Patients will be included during follow up, at approximately six to eight weeks from stroke onset, or later.

hiPSCs from five age-matched control subjects from our repository will be used as controls.

4.2 Inclusion criteria

In order to be eligible to participate in this study, a patient must meet all of the following criteria:

- Age \geq 18y
- Clinical and radiological diagnosis of acute ischemic stroke
- Admission to stroke unit
- Capability to provide written informed consent

4.3 Exclusion criteria

A potential subject who meets any of the following criteria will be excluded from participation in this study:

- Any relevant systemic disease that is expected to interfere with a patient outcome within six months, such as malignancy
- Any progressive neurodegenerative disease
- Severe aphasia (informed consent not possible)

4.4 Sample size calculation

Sample size calculation is hampered by lack of data. A sample size of ten patients and five controls is based on feasibility considerations: cell lines, culturing, and measurements of 15 subjects are possible within 2 years and provide a first estimation of the feasibility of the objectives.

5. TREATMENT OF SUBJECTS

Patients will be treated according to local and national guideline for ischemic stroke. There will be no experimental / additional treatment. Standard treatment or care will not be withheld.

6. INVESTIGATIONAL PRODUCT

Not applicable.

7. NON-INVESTIGATIONAL PRODUCT

Not applicable.

8. METHODS

8.1 Study parameters/endpoints

All study parameters will be collected from neuronal networks *in vitro*. Determinants will be collected from patients, all in the context of current care.

8.1.1 Main study parameter/endpoint

Primary outcome measure is network functionality, where a network is considered functional when a minimum of 1/3 of the electrodes shows activity, with a minimum of 6 spikes per minute per active electrode, and a minimum of one synchronous event per minute at eight weeks after plating.

8.1.2 Secondary study parameters

Electrophysiological responses to simulated 'cerebral ischemia', i.e. reduction of oxygen and glucose levels in the medium at eight to ten weeks after plating, as described previously.¹⁴

- Percentage reduction in network activity, functional connectivity, and synaptic responses (i.e. network responses to electrical stimulation of one electrode).
- Speed of reduction in network activity, functional connectivity, and synaptic responses.
- Extent of restoration of network activity, functional connectivity, and synaptic responses after restoration of oxygen and glucose levels.

8.1.3 Tertiary study parameters (potential factors that associate with ischemic responses)

Network and neuronal properties as studied by immunocytochemical analyses at eight weeks after plating.

- Excitation-inhibition ratio defined as the number of AAV-positive (excitatory) and AAV-negative (inhibitory) synapses
- Synaptic density, defined as the number of synaptophysin-positive puncta per neuron
- Apoptosis as visualized by Caspase 3/7 staining
- Cell death as visualized with propidium iodide

8.1.4 Determinants (potential clinical predictors of ischemic responses)

Demographic, baseline clinical and radiological parameters, and functional recovery of patients will be collected in the context of current care. Potential predictors of ischemic responses include age, sex, medical history, cardiovascular risk factors, stroke severity, medication, radiological stroke characteristics, and signs of small vessel disease. Also, data on final infarct size and functional recovery (modified Rankin Scale at three months) will be collected.

8.2 Randomisation, blinding and treatment allocation

Not applicable.

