12. ADMINISTRATIVE ASPECTS, MONITORING AND PUBLICATION

12.1 Handling and storage of data and documents

All patients will receive a study number by which all data will be coded. The study coordinator and the principal investigators will have access to the source data, if necessary. The code will be safeguarded by the study coordinator. The study data will be stored digitally and saved for 15 years.

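### Section 8.2 sets aside randomisation and blinding altogether, although the laboratory comparison of patient and control networks needs masked running and scoring and a balanced layout

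*Protocol*

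**What the plan says.** - Section 8.2, "Randomisation, blinding and treatment allocation", carries a single answer for all three items: not applicable. No reason is given.
- Section 3 describes the design: "This will be a prospective, experimental, case-control study in human blood".
- Section 4.1 fixes the groups: "Ten patients with ischemic stroke will be included in this study", and "hiPSCs from five age-matched control subjects from our repository will be used as controls". Section 4.4 adds: "A sample size of ten patients and five controls is based on feasibility considerations".
- Section 8.1.2 defines simulated ischemia as "reduction of oxygen and glucose levels in the medium at eight to ten weeks after plating". Section 8.3 places the networks on multiwell electrode arrays.
- Section 10.1 plans fifteen networks per subject in three independent batches. The primary endpoint is read by equipment and software against fixed thresholds and is only described.
- Section 10.2 tests ischemic responses between patients and controls. It also takes inter-patient variance above intra-patient variance as the sign that patients differ.
- Section 8.1.3 lists stain and count readings, for example "Synaptic density, defined as the number of synaptophysin-positive puncta per neuron". Section 10.3 relates these to ischemic responses.
- Section 12.1 says "All patients will receive a study number by which all data will be coded". It does not mention control lines or masking of laboratory staff.

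**The concern.** Treatment allocation is indeed not an issue, because section 5 rules out any experimental treatment. The laboratory work nevertheless involves assignments of its own: lines go to wells, plates and batches, and networks go to an ischemia run on some day within a two-week window. It also involves readings, such as puncta and synapse counts, in which the reader's expectation can play a part.

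Two features make group-linked differences plausible. Control lines already exist in a repository, while patient lines are made one after another from consecutively recruited patients (11.2) in a programme planned for two years (4.4). Nothing requires the two kinds of line to share plates, batches, run days or culture age at testing.

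Both secondary objectives are exposed. A plate, run-day or culture-age effect that follows group looks like a patient-control difference. One that follows the individual line looks like inter-patient variance. Extra networks per subject do not dilute an effect that acts in the same direction on all of them. Masking and layout are also matters of conduct: once experiments have been run unmasked and unbalanced, a later analysis plan cannot restore either.

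**Working it through.** **The protocol's own figures.** 10 + 5 = 15 subjects (4.1, 4.4). 15 × 15 = 225 networks (10.1), of which 10 × 15 = 150 are from patients and 5 × 15 = 75 from controls. The protocol has no power calculation to reproduce.

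**Reading the sections together.** Section 8.2 excludes randomisation and blinding. Sections 8.1.2 and 10.2 describe an imposed exposure followed by a group comparison, and 8.1.3 and 10.3 describe scored readings related to the response. No other section supplies masking or layout; 12.1 deals only with the coding of patient data.

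The calculations below are illustrations. The bias sizes, variance shares and 5% level are assumptions; none is in the protocol.

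**1. Patient versus control, subject-level t test.** If a bias of d subject-level SDs follows group and there is no true difference, the test statistic is noncentral t with 10 + 5 − 2 = 13 degrees of freedom and noncentrality d × √(10 × 5 / 15) = 1.826 d. The two-sided 5% critical value is 2.160.

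| Assumed d | Noncentrality | False-positive rate |
|---|---|---|
| 0 | 0 | 5.0% |
| 0.25 | 0.456 | 7.1% |
| 0.5 | 0.913 | 13.5% |
| 1.0 | 1.826 | 39.4% |

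**2. What layout does and coding does not.** Simulation with 4,000 runs, 15 subjects × 15 networks, between-subject SD 1, between-network SD 1 and no true difference. A position effect is either tied to group or spread at random over wells.

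| Position effect | Tied to group: mean bias, false positives | Random wells: mean bias, false positives |
|---|---|---|
| 0.25 | 0.25, 6.4% | −0.01, 5.4% |
| 0.5 | 0.50, 12.4% | 0.00, 5.0% |
| 1.0 | 1.00, 37.8% | 0.02, 5.1% |

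The group-tied column is the same whether or not samples are coded. Random placement removes the bias.

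**3. Inter-patient variance.** Take 10 patient lines × 15 networks, no true patient difference, and a one-way F test at 5% that ignores run. The critical value of F(9, 140) is 1.947. Let a share r of the variance be due to run.

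- One run per line: the F ratio is inflated by 1 + 15r/(1 − r). For r = 0.05 this is 1.789, so the false-positive rate is P(F > 1.947/1.789 = 1.088) = 37.5%. For r = 0.10 it is 2.667, giving P(F > 0.730) = 68.1%.
- Each batch of each line in its own run (5 networks per run), by simulation: about 12% for r = 0.05 and 22% for r = 0.10.

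The second case is closer to the three independent batches in 10.1; the first is an extreme. The protocol gives neither the run schedule nor the run variance.

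**The case against.** The strongest reply is that most readouts leave little room for judgement. This stands for the primary endpoint: its criteria are fixed numbers, applied by equipment and software, with no group test. The secondary responses are also electrode recordings, and a stable position effect on baseline activity would partly cancel in a percentage reduction. That answers assessor bias better than it answers run-day or culture-age effects on the response itself.

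It can also be said that scoring and plate-map rules belong in laboratory procedures that are not shown; section 8.3 refers to staining protocols available on request. That would be a fair reply to silence, but section 8.2 is not silent: it declares the matter not applicable. Section 10.2 names a two-way ANOVA without its factors, so batch or plate might be adjusted for. That would help only where these are recorded and not fully confounded with group or line.

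Four stronger readings are tempting and unsupported:

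- A reader might infer that staff know the group when they run and score experiments. Section 12.1 merely omits control lines; it does not say this.
- A reader might infer that patients and controls are compared on the image counts. No such test is stated; the counts enter only the associations with ischemic response, which a counter aware of group or response could still bias.
- A reader might infer that culture age at testing does differ by group. The protocol gives a window and no more.
- A reader might infer that coding alone would be enough. It does not touch position or run order.

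Finally, this is a feasibility study that makes no power claim, and full balance is hard when patient lines arrive sequentially. Both points temper the weight of the concern and shape the remedy.

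**Conclusion.** The concern holds in limited form. The not-applicable answer is right for treatment allocation and wrong for the laboratory experiment. As written, the plan leaves the secondary patient-control comparison, the inter-patient variance comparison and the tertiary associations open to effects of plate, batch, run day, culture age and unmasked scoring.

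The actual size cannot be estimated from the protocol. The illustrated false-positive rates show only what would follow if a bias or run variance of the assumed size were present; they are not evidence that one is. The primary endpoint is little affected. The point deserves correction before the experiments start, because masking and balance cannot be added afterwards.

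**What to change.** In section 8.2, limit the not-applicable answer to treatment allocation and add, for the laboratory work:

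- **Coding and masking.** Patient and control lines carry one common code series. Existing staff who run the ischemia experiments and score the stains and counts are masked to group, and scorers of stains also to ischemic response, as far as practicable until data lock.
- **Layout.** Plate position, run order and day of the ischemia experiment within the stated window follow a random list balanced by group as far as line availability permits, with control lines included in each plating round.
- **Recording.** Plate, batch and culture age at testing are recorded for every network.

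The cost is a code list, a plate map and some scheduling, including growing control lines alongside each round of patient lines. No extra patients, assays or assessors are needed. Balance will be incomplete because patient lines arrive one after another, and staff who derive the lines may still recognise them. Neither masking nor layout removes differences between existing repository lines and newly made patient lines; that limitation should be stated when the comparison is reported.

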8.3 Study procedures

Procedures in patients

All patients with acute brain infarcts will be admitted to a stroke unit to receive diagnosis and treatment as usual, as described in national and local stroke unit protocols. Standard CT or MRI, CT-angiography, CT-perfusion, and measures of neurological impairment and functional recovery are collected in the context of current care.

Patients will be informed about the study after admission on the stroke unit or at the time of follow up by the treating physician. If the patient gives permission, the treating physician will contact the research coordinator or study nurse. The research coordinator or study nurse will then contact the patient and provide additional information, both orally and written. The patient will be able to read the information carefully, discuss with family and ask questions. Patients will have at least one week to consider participation. . Inclusion will take place at the time of follow up, approximately six to eight weeks after infarction.

After oral and written informed consent, 30cc of venous blood in heparin anticoagulant (3x10cc) will be collected, handled, and stored according to local guidelines. Blood samples from patients will be collected during routine follow up at the hospitals outpatient department. Blood samples will be collected during routine blood sampling, if possible. If not, there will be one additional puncture. There will be no additional hospital visit.

Procedures in blood samples

Blood samples will be transported to University of Twente, CNPH lab, for further work-up and analysis. In short, we will generate iPSCs lines by exposing lymphoblast to reprogramming factors using a non-integrating episomal plasmid system to acutely express the Yamanaka reprogramming factors.^{15,16} hiPSC clones will be validated for pluripotency and genomic integrity through a standardized battery of quality control tests. iPS cells will be directly derived into excitatory and inhibitory neurons as published previously.¹⁷ Physiological ratios of excitatory and inhibitory neurons will be grown on Multiwell-MEAs for non-invasive, continuous recording of network functioning through extracellular electrodes. In parallel, cultures plated on coverslips will be fixed in 4% paraformaldehyde in 0.1M PBS at pH 7.4 for immunocytochemical staining (Figure 1). Staining protocols are available on request.

[figure not shown]

Figure 1. Examples. A) Multi-well multi-electrode array (MEA) plate; enlargement of one well with electrodes and neuronal network. B) Enlargement of micro-electrode with surrounding cultured neurons (upper) and spikes and burst recorded from this electrode (lower panel). C) Neurons (MAP2 staining, green) and astrocytes (GFAP staining, red) derived from hiPSCs of a healthy subject.

8.4 Withdrawal of individual subjects

Subjects can leave the study at any time for any reason if they wish to do so without any consequences. The investigator can decide to withdraw a subject from the study for medical reasons.

8.5 Replacement of individual subjects after withdrawal

Subjects will not be replaced after withdrawal.

8.6 Follow up of individual subjects after withdrawal

Subjects will be followed up after withdrawal.

8.7 Premature termination of the study

Not applicable.

9. SAFETY REPORTING

9.1 Temporary halt for reasons of subject safety

Not applicable.

9.2 AEs, SAEs and SUSARs

9.2.1 Adverse events (AEs)

Adverse events are defined as any undesirable experience occurring to a subject during the study, whether or not considered related to the study procedures.

We request permission to only report AEs that are related to blood sampling, such as bleeding or hematoma.

9.2.2 Serious adverse events (SAEs)

A serious adverse event is any untoward medical occurrence or effect that

- results in death;
- is life threatening (at the time of the event);
- requires hospitalisation or prolongation of existing inpatients' hospitalisation;
- results in persistent or significant disability or incapacity;
- is a congenital anomaly or birth defect; or
- any other important medical event that did not result in any of the outcomes listed above due to medical or surgical intervention but could have been based upon appropriate judgement by the investigator.

An elective hospital admission will not be considered as a serious adverse event.

We request permission to only report SAEs that are related to blood sampling, such as bleeding or hematoma.

The sponsor will report the SAEs through the web portal *ToetsingOnline* to the accredited METC that approved the protocol, within 7 days of first knowledge for SAEs that result in death or are life threatening followed by a period of maximum of 8 days to complete the initial preliminary report. All other SAEs will be reported within a period of maximum 15 days after the sponsor has first knowledge of the serious adverse events.

